### **8.2. Demographic and Other Baseline Characteristics**

Demographic characteristics such as gender, age, race, ethnicity, height, weight, BMI, time since first gout diagnosis and estimated glomerular filtration rate (eGFR) will be summarized for the ITT, the SS and the EPS population, by treatment and overall. Demographic characteristics will be listed for all randomized patients.

Age (years) will be calculated based on date of signed informed consent as:

(Date of informed consent - date of birth) / 365.25 and truncated to complete years

BMI (kg/m^2) will be calculated as: Weight (kg)/[Height(cm)/100]

### **8.3. Medical History**

Medical history will be coded using current version of Medical Dictionary for Regulatory Activities (MedDRA®). Medical history will be listed for all randomized patients. No summaries will be provided.

### **8.4. Other Baseline Characteristics**

Tophus assessment at screening, gout flare assessment at screening and baseline and the number of tender and swollen joints at baseline will be summarized by treatment group, overall SEL-212 and total. In addition, sUA at screening and baseline (Day 0 pre-dose) will be summarized by treatment group, as well as the change in sUA from screening to baseline. Disease severity of refractory gout will be characterized by:  $\geq 3$  gout flares within 18 months of Screening; presence of  $\geq 1$  gout tophus; and current diagnosis of gouty arthritis.

This document is confidential.

## **8.5. Medication**

Prior medication is defined as any medication which has an end date prior to the date of first dose of study drug administration.

Concomitant medication is defined as any medication which has an end date after the date of first dose of study drug administration or missing. Concomitant medication will be further classified as concomitant to the main phase of the study (TP1 to TP6) – these are all medications with start and/or end date after the first dose in the double blinded treatment phase and prior to first dose in the extension phase – and as concomitant to the extension phase of the study – these are drugs with end date after first dose in the extension phase. A respective flag will be presented in the patient listings.

The original verbatim terms collected in the eCRF for prior and concomitant medications will be coded using the World Health Organization Drug Dictionary (WHO-DD current version).

Listings will include the therapeutic (i.e., the second level of Anatomical Therapeutic Chemical [ATC] classification system code, that is, corresponding to the first 3 figures), preferred name (the fourth level of the ATC code, that is, corresponding to the first 5 figures) and verbatim text. The listings will be sorted by treatment group, patient id, chronological start date, stop date, therapeutic class, preferred name and verbatim name and will contain all randomized patients.

A frequency table of the number and percentage of patients will be provided for prior medications and concomitant medications by therapeutic class and preferred name for each treatment group and overall on the ITT population for the whole study, but also for the double blind treatment phase and the extension phase separately

Premedication for gout flare and premedication against infusion reactions (provided before start of dosing in each treatment period) will be summarized separately by treatment group and period, if applicable.

## **8.6. Summary of sUA from screening to baseline, stratified by ULT at screening**

An additional baseline summary will be produced, stratifying all randomised individuals by whether they were on ULT at screening or not. A summary of sUA at screening and baseline (Day 0 pre-dose) will be summarized by treatment group, as well as the change in sUA from screening to baseline.

This document is confidential.

## **9. Efficacy**

The confirmatory analysis of efficacy is described in Sections 9.2 and 9.3 and will be performed in the double-blind treatment period. Most of the efficacy assessments will continue during double-blind extension phase of the study (TP 7 to TP12) also, but they will be summarized using descriptive statistics only. Sections 9.3.3 and 9.3.4 present the additional secondary and exploratory endpoints and analyses for the double-blind treatment period. Section 9.3.5 lists the exploratory endpoints and analyses for the double-blind extension phase.

### **9.1. Assessment of sUA Time Curve and Summaries**

The sUA time curve with assessments at Day 0, pre-treatment (0 h), Day 0, post-treatment (4.5 h), Day 7, Day 14, Day 21 and Day 28 in TP6 will be used to estimate the proportion of time that the sUA level is below 6 mg/dL by Day 28. Based on the serum samples collected during TP6 an estimate of the time with sUA < 6 mg/dL can be determined by connecting each two neighboring data points with a straight line. If the sUA time curve goes above 6 mg/dL the linear interpolation method will be used to estimate the point in time at which the sUA time curve intercepts the line between the last sUA value < 6 mg/dL and the first value  $\geq$  6 mg/dL. The proportion of time that the sUA level is < 6 mg/dL will be computed by taking the ratio between the time during which the sUA level remains < 6 mg/dL (if necessary, using the linear interpolation method) and the entire time interval within TP6 by Day 28. Actual times will be plotted on the time curve, but only the interpolation of actual times up to Day 28 will be used. For example, if a patient had their Day 28 assessment on Day 30 then a straight line will connect Day 30 and their previous assessment, but the percentage of time the time curve is < 6 mg/dL will be derived only up to Day 28. If a point at Day 28 is not available on the curve (possibly due to an extension of TP6 for reasons such as presenting mild-moderate COVID-19 symptoms), then the next available assessment between Day 28 and up to, and including Day 0, pre-treatment (0 h) in TP7 will be used to interpolate the curve up to Day 28. This can include the use of unscheduled sUA assessments. For example, if a patient is missing their Day 28 assessment, and the next assessment is at Day 0, pre-treatment (0 h) in TP7 then this additional timepoint will be plotted as the time in days from Day 0 in TP6. A straight line will be connected between this and the last assessment in TP6 and the percentage of time the time curve is < 6 mg/dL will be derived up to Day 28. Further, if the same patient has an unscheduled visit on Day 40 of TP6 (e.g., once their mild-moderate COVID-19 resolve) then the straight line will be connected between this and their previous assessment in TP6 prior to Day 28 (as Day 40 is now the next available assessment between Day 28 and up to, and including Day 0, pre-treatment (0 h) in TP7) and the percentage of time the time curve is < 6 mg/dL will again be derived up to Day 28. If there are no such assessments available, but the use of unscheduled assessments allows the extension of the time curve from the last scheduled assessment prior to Day 28 then these can also be used. For example if a patient has all scheduled assessments during TP6 up to Day 21, with no assessments on or after Day 28, up to and including Day 0, pre-treatment in TP7, but has an unscheduled assessment on Day 25 then the percentage of time with sUA level < 6 mg/dL for TP6 would be taken to be the percentage of time the sUA levels were < 6 mg/dL from Day 0 to Day 25. If only 2 or fewer assessments are available (allowing for the use of assessments after Day 28 up to, and including Day 0, pre-treatment (0 h) of TP7, and further unscheduled assessments prior to Day 28), and the first and last attended assessments are less than 7 actual days apart, then the response evaluation of TP6 will be missing. For a patient to be considered a responder in TP6, the proportion of time that the SUA level is < 6 mg/dL (i.e., percentage of nonhyperuricemic time) during TP 6 by Day 28 (or last available assessment prior to Day 28 if no

This document is confidential.

assessments are available from Day 28 up to, and including Day 0, pre-treatment (0 h) in TP7) must be at least 80%.

For example, if a patient only has measurements on both Day 0 assessments and Day 8 (planned assessment for Day 7) then percentage of time with sUA level < 6 mg/dL for TP6 would be taken to be the percentage of time the sUA levels were < 6 mg/dL from Day 0 to Day 8. However, if the Day 7 planned assessment was taken on Day 6 then this patient would have a missing value for their response.

A frequency table of the percentage of responders in TP6 will be provided by treatment group in overall and stratified by tophus status at baseline for the ITT population. Additionally, a summary table with the total and percentage of time a patient has sUA values < 6 mg/dL in TP6 will be provided by treatment group in overall and stratified by tophus status at baseline for the ITT.

Summary table of the actual values and change from baseline for sUA results will be provided for each scheduled sampling time point – including extension phase - by treatment group. Additionally, mean sUA level, reduction in mean sUA and percent reduction in mean sUA from baseline during TP6 will be presented by treatment group.

- Mean sUA level is defined as the area under the sUA time curve (computed using the linear trapezoidal rule during Treatment period 6) divided by the corresponding time interval.
- Reduction in mean sUA is computed by subtracting baseline sUA level from mean sUA during Treatment period 6.
- Percent reduction in the mean sUA from baseline is computed as the mean sUA level during Treatment period 6 minus baseline sUA level divided by baseline sUA level multiplied by 100

The SUA levels will be visualized in a box-plot by assessment time and treatment.

## **9.2. Analyses of Primary Efficacy Estimands**

The statistical testing of each SEL-212 treatment group versus placebo in all four estimands will be performed using the Mantel-Haenszel (MH) estimate and test for common risk difference considering the randomization stratum of tophus presence (yes/no) with a two-sided type 1 error rate  $\alpha = 2.5\%$  to adjust for the two comparisons against placebo. Only the test results of the main estimand will be considered as confirmatory.

In addition, a logistic regression model will be fitted, with response as the outcome variable, tophus presence (yes/no) at baseline, treatment group included as covariates.

The analysis of all four estimands will be carried out based on the ITT population, and analyses on the main, second and third estimand will be performed, but the population will be changed to the mITT, the PP and the all randomized set, as opposed to the ITT.

For missing response evaluation data in TP6 (see also Section 9.1) values will be multiple imputed. The logistic method considering the tophus status at baseline and the treatment group will be applied for the multiple imputation.

For the main, second and fourth estimand of primary efficacy, sensitivity analysis will be performed using the tipping-point analysis for binary response, to investigate the sensitivity to departures from missing-at-random (MAR). For patients with missing response status, the underlying response probability will be varied systematically and comprehensively such that, should one exist, a tipping point can be identified where if

This document is confidential.

the probability of being a non-responder in the treatment group is higher than in the placebo group, the statistical significance switches from treatment effect p-value  $<0.025$  to treatment effect p-value  $\geq 0.025$ . For each arm, the following scenarios will be explored, where the true underlying response probability amongst those with missing response status will have the following probabilities:

0.01, 0.11, 0.21, 0.31, 0.41, 0.51, 0.61, 0.71, 0.81, 0.91, 0.99.

The analysis will be performed in each combination of placebo probability to SEL-212 active treatment arm probability, with the most extreme cases being when one arm in the comparison has a response probability of 0.99 and the other has a response probability of 0.01. Once a tipping point has been established, scenarios that make the treatment effect more favorable to the placebo arm will not be examined. Responses for those with missing response data will be imputed multiple times for each scenario, with responses drawn with the probabilities listed above. In each scenario, the results across multiply imputed datasets will be combined in the same way as the multiple imputation analysis, but the response probabilities will be pre-specified as opposed to generated from a logistic regression.

An  $11 \times 11$  table will be displayed for each SEL-212 active arm vs. placebo comparison where the p-values from the tipping point analysis under each combination of underlying response probabilities for those with missing data are shown.

A table with number and type/reason of missing values in the primary efficacy variable will be provided by treatment group on the ITT population for each estimand.

Frequency table of the treatment responders considering the responder definition in Section 9.1 but also the definitions in Section 6 for the estimands of interest will be provided by treatment group for all four estimands defined in Section 6, and the difference in proportions between each SEL-212 treatment group and placebo will be presented together with 97.5% confidence intervals. The treatment effect odds ratio and 97.5% confidence intervals will be presented from the logistic regression.

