13.1 Sample Size Determination

The primary efficacy criterion in this study is defined as the percentage of the patients who achieve and maintain reduction of sUA < 6 mg/dL for at least 80% of the time during Treatment Period 6 by Day 28.

The sample size estimation is based on the main estimand for the primary efficacy criterion from version 5.0 of the protocol. This estimand considered all patients who discontinue study treatment due to lack of efficacy (e.g., meeting stopping rule), due to treatment-related or non-treatment related AE as treatment failures, as well as initiating prohibited medication that lowers sUA, withdrawal of consent or lost to follow up for reasons other than COVID-19.

Based on the results in the Phase 2 study (SEL-212/201) with SEL-212, the responder rate in all randomized and dosed patients is assumed to be 45% in SEL-212. For placebo, a responder rate of 5% is assumed. Considering a randomization ratio of 1:1:1 for SEL-212A and SEL-212B against placebo, a statistical power of 90%, a two-sided alpha-level of 2.5% and using the Chi-square test with continuity correction for the 2 pairwise comparisons of each SEL-212 dose group against placebo, 32:32:32 randomized and dosed patients will be required for each treatment group. Considering the potential that some randomized patients will terminate the study early (approx. 8%), the number of the patients required to be randomized and dosed in total is 105 (i.e., 35:35:35) to demonstrate efficacy.

Randomized but not treated subjects will be replaced. For the sample size estimation, the Chi-square test is used instead of the Mantel-Haenszel test, although the randomization will be stratified for tophus presence (yes/no), as there is no valid assumption of the distribution of this stratification variable within the eligible patient population.

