### **3.5. Determination of Sample Size**

The sample size estimation is performed for the main estimand for the primary efficacy endpoint from V5.0 of the protocol 'percentage of patients who achieve and maintain reduction of sUA < 6 mg/dL for at least 80% of the time during Treatment Period 6 by Day 28' which defined in Section [6.1](#). This estimand considered the following as treatment failures: patients who discontinue study treatment due to lack of efficacy (eg, meeting stopping rule), patients who discontinue study treatment due to treatment-related or non-treatment related AEs, patients who take prohibited medication that lowers sUA, or patients who are lost to follow up or withdraw consent for reasons other than COVID-19.

Based on the Phase 2 (protocol SEL-212/201) results with SEL-212, the responder rate in all randomized and dosed patients is assumed to be 45% in SEL-212. For placebo a responder rate of 5% is assumed. Considering a randomization ratio of 1:1:1 for SEL-212A and SEL-212B against placebo, a statistical power of 90%, a two-sided alpha-level of 2.5% and using the Chi-square test with continuity correction for the 2 pairwise comparisons of each SEL-212 dose group against placebo, 32:32:32 randomized and dosed patients will be required for each treatment group. Considering the potential that some randomized patients will terminate the study early (approx. 8%), the number of the patients required to be randomized and treated in total is 105 (i.e., 35:35:35) to demonstrate efficacy. Randomized but not treated subjects will be replaced. For the sample size estimation, Chi-square test is used instead of the Mantel-Haenszel test, although the randomization will be stratified for tophus presence (yes/no), as there is no valid assumption of the distribution of this stratification variable within the eligible patient population.

From an amendment in version 6.0 of the protocol, the main estimand for the primary efficacy criterion was updated to include patients who present a positive COVID-19 test along with severe or critical symptoms of COVID-19, and patients who missed all assessments of sUA during TP6, as treatment failures. As these are expected to be unrelated to the treatment, then assuming that the number of additional treatment failures to each arm would be roughly equal, the difference in response rates can still be assumed to be 40%, unless the treatment failure rate due to positive COVID-19 tests along with

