## **7. General Aspects for Statistical Analysis**

### **7.1. General Methods**

SAS® version 9.4 or higher will be used for all statistical analyses and tabulations.

In general, summaries will present data by treatment group and overall for each scheduled assessment time where appropriate.

Unless stated otherwise, descriptive summaries will include n, mean, standard deviation, median, minimum and maximum for continuous variables, and n and percent for categorical variables. If there are multiple assessments collected for the same scheduled time the first assessment post-baseline will be used. The last available assessment before start of study treatment will be used as baseline.

Adverse events and medical history will be coded according to the most recent version of Medical Dictionary for Regulatory Activities (MedDRA). Prior and concomitant medications will be coded using the most recent WHO Drug Dictionary version. The actual version of MedDRA and WHO drug used will be noted in the footnote of the respective output.

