will be included in the analysis. In addition, the logistic model used to carry out multiple imputation for missing response evaluation data in TP6 will only include the treatment group in the model (and not tophus status at baseline), as only patients with tophus at baseline will be included in the analysis.

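### The logistic imputation of missing TP6 response has no safeguard for a placebo arm with no observed responders, an event of about 13–17% probability at the plan's own 5% placebo rate

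*SAP*

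**What the plan says.** For the multiple imputation of the primary endpoint SAP 9.2 states: "The logistic method considering the tophus status at baseline and the treatment group will be applied". For key secondary 5, the same response in patients with tophi at baseline, SAP 9.3.2.5 states that "the logistic model used to carry out multiple imputation for missing response evaluation data in TP6 will only include the treatment group". SAP 9.3.2.4 also uses a treatment-only logistic imputation for key secondary 4 (tophus response).

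On software, SAP 7.1 says only "SAS® version 9.4 or higher will be used for all statistical analyses and tabulations". No section gives a penalty, an augmentation, a prior, a fallback for an arm without responders, or the number of imputations.

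The planning rates are in SAP 3.5: "the responder rate in all randomized and dosed patients is assumed to be 45% in SEL-212" and "For placebo a responder rate of 5% is assumed". Protocol 13.1 agrees. The tipping-point analysis in SAP 9.2 replaces the logistic model with fixed response probabilities from 0.01 to 0.99, but it is a sensitivity analysis. The confirmatory p-value comes from the logistic imputation.

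**The concern.** A logistic model with a treatment term needs at least one responder and one non-responder in each arm. If every observed placebo patient is a non-responder, the likelihood keeps rising as the placebo log-odds fall, so there is no finite maximum (separation). The software reports a large negative estimate with a huge standard error, and both depend on where the iterations stop. Imputation draws from that distribution give response probabilities near 0 or near 1. Missing placebo patients are then imputed as responders at a rate unrelated to the data.

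At stake are the size of the estimated difference, its standard error and the confirmatory p-value. For key secondary 5 a failed test also ends confirmatory testing of key secondaries 6 to 9 for that dose (SAP 9.3.1).

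**Working it through.** **1. The plan's own figure.** Inputs from SAP 3.5: 45% v 5%, and "a statistical power of 90%, a two-sided alpha-level of 2.5% and using the Chi-square test with continuity correction".

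- z(0.9875) = 2.241, z(0.90) = 1.282, mean rate 0.25.
- Uncorrected n = [2.241·√(2·0.25·0.75) + 1.282·√(0.45·0.55 + 0.05·0.95)]² / 0.40² = 26.7.
- Continuity correction: (26.7/4)·[1 + √(1 + 4/(26.7·0.40))]² = 31.5, so 32 per arm.
- Inflation for 8% early termination: 32/0.92 = 34.8, so 35.

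Both figures reproduce. The final target is 40 per arm. With 8% missing, 0.92 × 40 ≈ 37 are observed and 3 are missing.

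**2. Chance of no observed placebo responder**, 0.95ⁿ:

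| Observed placebo n | Probability |
|---|---|
| 40 | 12.9% |
| 37 | 15.0% |
| 35 | 16.6% |
| 24 (tophi subset, 60% of 40) | 29.2% |
| 22 (tophi subset) | 32.4% |

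**3. What the fit does.** The model (intercept, tophus status, two arm terms) was fitted by Newton-Raphson with 37 observed per arm and no placebo responders.

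| Iterations | Placebo intercept (SE) | Mean imputed placebo response |
|---|---|---|
| 8 | −9.1 (16) | 29% |
| 15 | −16.1 (542) | 49% |
| 25 | −26.1 (80,000) | 50% |

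The last column is roughly the chance that a normal draw of the intercept is positive: Φ(−9.1/16) = 0.28, and Φ(−16.1/542) = 0.49. A relative-gradient criterion of 1e-8 is met at iteration 17, at about 49%. Near convergence, each imputation makes nearly all or nearly none of the missing placebo patients responders.

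An augmented-data fit gives an intercept of −3.9 (SE 1.2) and imputes 3–4%. With a single placebo responder the plain fit is already finite and imputes 4–5%. The treatment-only model in the tophi subset gave 48–52% (plain) v about 5% (augmented).

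**4. Effect on the primary test.** No placebo responders, 40 per arm, Mantel-Haenszel risk difference, 200 imputations, Rubin's rules:

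| Missing per arm | Active responders | Plain: difference (SE), p | Augmented: difference (SE), p |
|---|---|---|---|
| 3 | 17/37 | 0.425 (0.095), <0.001 | 0.459 (0.083), <0.001 |
| 3 | 9/37 | 0.208 (0.086), 0.016 | 0.242 (0.072), <0.001 |
| 3 | 7/37 | 0.155 (0.081), 0.056 | 0.188 (0.066), 0.004 |
| 8 | 14/32 | 0.330 (0.142), 0.021 | 0.431 (0.089), <0.001 |
| 10 | 14/30 | 0.338 (0.163), 0.038 | 0.455 (0.094), <0.001 |

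In the first row the loss is 0.459 − 0.425 = 0.034. This agrees with the extra imputed responders: (0.475 − 0.035) × 3/40 = 0.033.

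**5. Key secondary 5.** With 24 per arm, 3 missing, no placebo responders and 7/21 active responders, the pooled risk difference gave p = 0.034 (plain) v 0.002 (augmented). The SAP tests with a continuity-corrected chi-square and does not say how to pool it, so these p-values are approximate. This case has 3/24 = 12.5% missing and 7/21 = 33% response. At a true 45%, seven or fewer of 21 has binomial probability 0.197.

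**The case against.** The strongest counter-argument is that this rarely matters.

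- **Probability.** At 13–17%, roughly six trials in seven would not meet the problem. This stands. The event is realistic but not likely.
- **Consequence.** In simulations at 45% v 5% with 3 missing per arm, power given no observed placebo responder was 100% with either fit; unconditionally it was 99.1% (plain) v 99.0% (augmented). With 5 missing, conditional power was 97.7% v 100%. Active 7/37 has probability 0.0008 at a true 45%, and 8 or 10 missing of 40 is 20–25%, against a planned 8%. This stands too. A reader might infer that the primary result is in danger under the planning assumptions, and the figures do not show that. Nor is there a risk of a false efficacy claim, because the error favours placebo.
- **Who is imputed.** Protocol 13.1, SAP 3.5 and the sample-size paragraph in SAP 6.1 describe the version 6.0 main estimand as counting patients with no TP6 sUA as failures. If that applies, few patients reach the imputation. But the failure lists in Protocol 13.4.1 (version 6.1) and SAP 6.1 do not include them, so the documents leave it open. Other rules also shrink the missing set: composite failures, visits continued after stopping drug, and use of unscheduled samples.
- **Software.** The SAP does not prescribe an unaugmented fit. A reader might infer that the plan names a method that must impute half. It names a method without the setting that decides between about 3% and about 50%.
- **Key secondary 4.** The 5% rate is for sUA response. No placebo rate is given for tophus response, so the probabilities above cannot be carried over.

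The tipping-point grid and the table of missing values by arm would make the distortion visible, but they would not replace the confirmatory p-value.

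**Conclusion.** The point holds as a gap in specification with a real but bounded effect. In the 13–17% of trials with no observed placebo responder (29–32% in the tophi subset), an unaugmented, converged fit biases the difference downwards by about 3 points with 3 missing per arm and raises the standard error from about 0.08 to 0.09.

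The primary conclusion survives at 45% v 5% with about 8% missing. In the cases run, significance at 0.025 was lost with a much smaller effect (7/37) or with 25% missing (p = 0.038). With 20% missing it was close (p = 0.021). Key secondary 5 is more exposed, because its arms are smaller and failure closes the hierarchy, although the reversal shown there needs a response below 45% and more than 8% missing.

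These results assume equal missingness across arms, a 60:40 tophus split within arms, the whole 8% being imputed, and normal draws from the fitted coefficients. Stopping the fit at 8–10 iterations gives about 29–40% instead of half.

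**What to change.** Before unblinding, add one sentence to SAP 9.2 and 9.3.2.5 specifying an augmented-data (penalised) likelihood for the logistic imputation. Add it to 9.3.2.4 as a precaution, since no placebo rate is given for tophus response. A remedy chosen after the placebo arm is seen to have no responders would be post hoc.

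Reconcile Protocol 13.1 and SAP 3.5 and 6.1 (sample-size text) with the failure lists in Protocol 13.4.1 and SAP 6.1, so that it is clear whether patients with no TP6 sUA are failures or are imputed.

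The cost is one programming option and a few lines of text. The downside is slight shrinkage of the imputed probabilities when every arm has responders. A Firth penalty for the supportive logistic regression in 9.2 is optional: its odds ratio would also be non-estimable if the placebo arm had no responders after imputation, but it is not the confirmatory test.
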